6.5.1 Assessment Schedule

All patients will complete a full assessment battery at baseline, *prior* to treatment. Patients will then complete a brief assessment battery at week 2, week 4, week 6, and then every 12 weeks (see Table 4).

Table 4: Data collection sessions for psychosocial measures

BASELINE	FOLLOW-UP

 • FACT • SF-12 • Depression (CES-D) • Social Provisions Scale • History of depression • FMCS 	
 • FACT • SF-12 • CES-D • FMCS

Several measures used previously in our work on chronic stress and QOL will be used in the proposed study. In all cases, they have proven to be useful and sensitive measures of stress and QOL, have proven to be stable, reliable, and valid with groups of people who are and are not suffering from major depression or other psychiatric disorders. All surveys will be completed electronically using e-tablets and response data will be collected using the HIPAA-compliant Qualtrics software platform.

Quality of Life:

The Functional Assessment of Cancer Therapy (FACT) is a cancer-specific measure of *health-related quality of life*. This instrument was able to discriminate between individuals with metastatic and non-metastatic disease, as well as between patients at different stages of illness. The scale has been found to have good concurrent validity, high internal consistency (0.89), and good test re-test reliability (0.82 to 0.88). The FACT will be completed at each assessment.

General QOL – General QOL will be assessed using the Medical Outcomes Study 12-item short-form survey (SF-12). Responses are based on a Likert-type scale. The SF-12 is a health-related QOL measure that is responsive to minor versus major medical problems as well as psychiatric problems. It has good test-retest reliability (coefficients for various subscales range from 0.60 to 0.81) and good internal consistency (coefficients range from 0.78 to 0.93). The SF-12 will be completed at each assessment.

Proprietary of MD Anderson Cancer Center

Depression:

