- Optional: on the 4th week (\pm 3 days) of therapy on protocol (following at least 1 infusion of nivolumab): collect blood samples for immune testing and correlative studies to assess treatment response to combination therapy.

Proprietary of MD Anderson Cancer Center

10.4 Imaging scans (CT of chest and CT scan or MRI of abdomen/pelvis) will be performed to determine disease response at 6 weeks (42 days)(+/- 3 days), 12 weeks (84 days +/- 7 days), and every 12 weeks (84 days +/- 7 days), for as long as patients are receiving therapy on protocol. A follow-up CT or MRI of the brain will only be ordered if clinically indicated.

10.5 Echocardiogram will be obtained on the 12th week (\pm 14 days) of therapy on protocol and then repeat every 6 months (\pm 1 month) or as clinically indicated.

10.6 Complete e-tablet QOL assessments (FACT, SF-12, CES-D, FMCS) at 2 weeks (\pm 7 days), 6 weeks (\pm 7 days), 12 weeks (\pm 7 days) and every 12 weeks (\pm 7 days) thereafter.

10.7 End of Treatment Evaluation: Adverse events and tumor-related signs and symptoms will be assessed. For patients who develop toxicity related to study drug necessitating discontinuation of protocol therapy before restaging to assess tumor response, physicians treating these patients will make every effort to repeat the appropriate imaging studies if feasible and indicated to assess tumor response at the time the patients are taken off protocol treatment. For patients taken off protocol therapy due to disease progression, blood samples and tumor biopsy (optional at the physician's discretion) will be collected within 28 days from the time that disease progression is first confirmed and used for immune testing and correlative studies.

10.8 Long-term Follow-Up: Patients will be followed for survival every 3 months (90 days \pm 1 month or 28 days) by record review or telephone correspondence. Patients in long term follow up at the time of Long Term Extension Phase approval will be assessed for survival every 6 months (180 days +/- 1 month or 28 days)

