- l. After 2 weeks (\pm 3 days) of MGCD516 monotherapy: collect fresh biopsy (optional at the physician's discretion) to assess treatment response to MGCD516 monotherapy
- m. Within 28 days of study entry
- n. Within 14 days (+/- 3 days) of study entry
- o. If urine protein \geq 100 mg/dL on urinalysis then obtain random urine protein/creatinine ratio
- p. Patients will continue to receive MGCD516 daily until disease progression or unacceptable treatment-related toxicity
- q. Patients will receive nivolumab as a 60 \pm 15 minute IV infusion on Day 1 of a treatment cycle every 2 weeks until disease progression or intolerance. Patients may be dosed no less than 12 days from the previous dose. Patients who have received at least 6 infusions of nivolumab 240 mg IV every 2 weeks with no DLTs related to nivolumab, will have the option to transition to the equivalent nivolumab schedule of 480 mg IV every 4 weeks.
- r. On the 4th week (\pm 3 days) of therapy on protocol (following at least 1 infusion of nivolumab): collect blood sample (optional at the physician's discretion) for correlative studies to assess treatment response to combination therapy
- s. On the 6th week (\pm 3 days) of therapy on protocol (following at least 2 infusions of nivolumab): collect blood sample for correlative studies to assess treatment response to combination therapy
- t. On the 6th week (\pm 3 days) of therapy on protocol (following at least 2 infusions of nivolumab): collect fresh biopsy (optional at the physician's discretion) to assess treatment response to combination therapy
- u. Obtain an echocardiogram on the 12th week (\pm 14 days) of therapy on protocol and then repeat every 6 months (\pm 1 month)
- v. In patients taken off therapy due to disease progression, collect blood sample for correlative studies to assess causes of disease progression
- w. In patients taken off therapy due to disease progression, collect fresh biopsy (optional at the physician's discretion) to assess causes of disease progression.
- x. Complete e-tablet QOL assessments (FACT, SF-12, CES-D, Social Provisions Scale, FMCS, History of Depression) within 14 days (+/- 7 days) of study entry
- y. Complete e-tablet QOL assessments (FACT, SF-12, CES-D, FMCS) at 2 weeks (\pm 7 days), , 6 weeks (\pm 7 days), 12 weeks (\pm 7 days) and every 12 weeks (\pm 7 days) thereafter

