14.3 Additional analyses

Demographics: For each treatment group (control, experimental), summary statistics will be provided for age, baseline disease status and prior treatments.

Toxicity: Adverse effects that will be evaluated include, but are not limited to infections, renal toxicity, hepatic toxicity, and pulmonary toxicity. Methods of assessment will include monitoring blood counts, and performing laboratory tests as indicated by clinical signs and symptoms. Evidence of toxicity or adverse events will be recorded at all clinic visits. All observed adverse effects will be graded for all patients and the degree of association of each with therapy assessed.

Quality of Life: Prior to inferential procedures, extensive descriptive analyses will be conducted for each of the measures obtained at each session. Descriptive statistics (e.g., means, ranges, standard deviations) will be computed, together with ninety-five percent confidence intervals for the means. Proportions of subjects falling outside normative ranges for the stress and QOL measures will also be calculated. Values for the standardized scales will be compared to normative data and patients receiving other types of cancer therapy. Graphical methods (e.g., boxplots and histograms) will be employed to more closely examine the distributions of the measures at each time point. Change scores for the stress and QOL measures will be computed as the simple differences between the baseline measure and subsequent evaluations. Bivariate associations between the raw scores, the change scores, optimism, social support, and demographic variables will be evaluated using Pearson's product moment correlation coefficients together with scatterplots where appropriate. These procedures will allow us to thoroughly characterize the stress and QOL profiles of this patient population across the sessions.

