In this study, numerous models will be constructed to analyze the data and, therefore, the results will be treated as hypothesis generating and interpreted with caution. Inferential statistics will comprise paired t-tests of the stress and QOL measures. Significant test results ($p < .05$) will be interpreted as indicating significant changes in stress and QOL associated with the treatment. Linear regression analyses will then be used to construct prediction models using a composite stress and QOL score. In these analyses, the composite stress and QOL score will be regressed onto spirituality and social support at the start of the trial, and interaction terms will be calculated to determine whether these factors moderate stress and quality of life. Potential confounders include the stress and QOL measures obtained at baseline and demographic and treatment characteristics. Backwards step-wise regression will be employed to construct the final models, with a rejection criteria of $p > .05$. Multivariate methods, including repeated measures analyses, will be employed to further explore the potential changes in the stress and QOL measures over time. Standard residual based diagnostic procedures will be used to evaluate model assumption and normalizing transformation made as appropriate.

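### Section 14.3 labels the quality-of-life results hypothesis generating, yet reads any unadjusted paired t-test with p<.05 as a treatment-associated change

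*Combined protocol and SAP*

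**What the plan says.** Sections 2.0 and 14.1 list QOL among the secondary objectives and outcomes. Section 14.3 describes the analysis in this order:

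- Descriptive statistics at each session, with 95% confidence intervals for the means.
- Change scores: "Change scores for the stress and QOL measures will be computed as the simple differences between the baseline measure and subsequent evaluations".
- A caution, given because many models will be fitted: "the results will be treated as hypothesis generating and interpreted with caution".
- The tests: "Inferential statistics will comprise paired t-tests of the stress and QOL measures".
- How to read them: results with p<.05 "will be interpreted as indicating significant changes in stress and QOL associated with the treatment".
- Regression and repeated-measures modelling.

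On the schedule, Section 10.6 reads "Complete e-tablet QOL assessments (FACT, SF-12, CES-D, FMCS) at 2 weeks" and continues with weeks 6 and 12 and every 12 weeks after that. Note y of the study calendar agrees. Section 6.5.1 differs: "Patients will then complete a brief assessment battery at week 2, week 4, week 6, and then every 12 weeks".

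The plan does not state how many paired t-tests will be run, and it specifies no multiplicity adjustment for them. It names no leading scale or visit.

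**The concern.** An analyst cannot fully follow both sentences. The caution says how to regard the results but sets no limit on what may be claimed. The p<.05 sentence is specific, so it is the one likely to be carried out. Applied over a grid of scales and visits, it makes at least one nominally significant change likely even if nothing changed. Such a result could then be reported as an effect of the combination on QOL. The problem comes from the number of tests and would remain with complete follow-up.

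**Working it through.** The plan gives no family-wise error rate, test count or QOL power, so there is no stated figure to reproduce. Only the per-test .05 is given; I take it as two-sided.

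**Number of tests (derived).** Four instruments are repeated at follow-up: FACT, SF-12, CES-D and FMCS. I assume one score each and one baseline comparison per visit, on the Section 10.6 schedule.

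- Weeks 2, 6, 12: 4 × 3 = 12
- Adding week 24: 4 × 4 = 16
- Adding weeks 36 and 48: 4 × 6 = 24

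The week 4 visit in Section 6.5.1, or subscale scoring, would add more. With week 4 the 24 becomes 4 × 7 = 28.

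**Expected nominal hits with no true change.** 12 × .05 = 0.6; 24 × .05 = 1.2.

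**Chance of at least one, independent tests.** 1 − .95^k:

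- k = 12: 46.0%
- k = 16: 56.0%
- k = 24: 70.8%

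**Chance of at least one, structured correlation.** The documents give no correlations. I assume .6 between any two visits of one scale, baseline included, and .3, .5 or .7 between scales. With unit variance, a change score has variance 2(1 − .6) = .8. Two changes sharing a baseline have covariance .6 − .6 − .6 + 1 = .4, hence correlation .4/.8 = .5. Different scales at different visits then correlate at .15 to .35. Simulated paired t-tests (n = 42, no dropout, 20,000 replicates per setting) gave:

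| Tests | Between-scale .3 | .5 | .7 |
|---|---|---|---|
| 12 | 39.9% | 36.3% | 30.7% |
| 16 | 47.4% | 43.2% | 36.6% |
| 24 | 58.7% | 54.0% | 47.6% |

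Smaller runs with the same settings reached 60.0% at the top, so I quote about 31% to 60%.

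**Chance of at least one, all tests equally correlated.** By numerical integration over one common factor:

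| Tests | ρ = .3 | ρ = .5 | ρ = .7 |
|---|---|---|---|
| 12 | 39.7% | 31.9% | 23.2% |
| 24 | 59.5% | 45.8% | 31.1% |

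Sample size hardly matters. Simulated independent tests gave 46.0% and 71.7% at n = 42 (12 and 24 tests), against 46.4% and 70.9% at n = 60.

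**Cost of adjusting one contrast per scale.** Four contrasts under Holm start at .05/4 = .0125. For 80% power at n = 42, the normal approximation gives (1.96 + 0.84)/√42 = 0.43 SD of the change score at .05, and (2.50 + 0.84)/√42 = 0.52 SD at .0125. Using the t distribution, these become 0.44 and 0.54 SD. The 0.54 is an upper limit, because later Holm steps are less strict.

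**The case against.** The best defence is that the plan already sees the problem. It gives the number of models as its reason for caution, and that sentence can be read as governing the whole paragraph, so that p<.05 merely marks a nominal change within an exploratory analysis. Section 14.3 also plans 95% intervals for the means, plots and repeated-measures analyses. Whether exploratory secondary outcomes need family-wise control is debatable. Most of this stands. It limits the weight of the point and argues for a wording change in place of formal error control. It does not remove the conflict, because the p<.05 sentence carries no qualifier and the planned intervals are for means, not explicitly for changes.

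Three stronger readings are tempting, and the documents do not support them.

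- **That a third to over half of the QOL findings would be false.** Each test still errs at 5%. The percentages are the chance of at least one hit, in either direction, somewhere in the grid when nothing has changed on any scale at any visit.
- **That the dose conclusion is compromised.** Section 3.4 compares 120 mg with 80 mg on depression, quality of life and hope at 3 months by Bayesian posterior probabilities, not by these t-tests. The Lo-EffTox rules in Section 14.1 use toxicity and response only.
- **That a week-12 contrast with Holm adjustment could now be prespecified.** Section 3.4 already reports 3-month QOL results for this trial, so choosing that time point today would be post hoc.

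**Conclusion.** The point holds as a minor problem of interpretation in a secondary outcome. Within one paragraph the plan calls the results hypothesis generating and tells the analyst to read any unadjusted p<.05 as a change associated with treatment. The chance of at least one such result with no true change depends on assumptions that the documents do not supply: the test count, one score per instrument, and the correlations. For 12 to 24 tests it is about 31% to 60% under the structured correlations, 46% to 71% under independence, and 23% at the lowest setting tabulated. Every one of these is well above 5%, so the conclusion does not hang on a particular choice.

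**What to change.** Replace the p<.05 sentence in Section 14.3 so that it agrees with the hypothesis-generating label. For example:

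> For each scale and follow-up visit, the mean change from baseline will be given with a 95% confidence interval. The number of comparisons made will be stated. Any p-values are nominal and unadjusted, and no claim of a significant treatment-associated change will rest on them.

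To make that number definite, reconcile the week 4 assessment between Section 6.5.1 and Section 10.6, and state which score of each instrument is analysed.

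A baseline to week-12 contrast per scale with Holm adjustment over the four may be shown as well, if it is labelled post hoc. Its detectable change at n = 42 is at most about 0.54 SD, against 0.44 SD unadjusted.

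The cost is a change of SAP wording and the loss of significance claims for QOL change. No new data are needed.

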15.0 DATA AND PROTOCOL MANAGEMENT

Protocol Compliance: All required interim and pretreatment data should be available, and the physician must assess tumor response and must provide a detailed description of toxicity, when appropriate. If dose modifications or treatment interruptions are necessary, the details must be carefully documented. Performance status must be documented at each toxicity assessment.

Data Capture: Data will be entered in the MD Anderson institutionally approved database(s). Registration data entry will occur prior to initiation of therapy. All eligibility criteria must be satisfied.

Accuracy of Data Collection: The MD Anderson Principal Investigator will be the final arbiter of response and toxicity, should a difference of opinion exist.

Monitoring: The trial will be monitored throughout the study with the assistance of the MD Anderson IND office. The study will be performed in accordance with ethical principles and follow federal, institutional, and departmental policy and or regulation. Every effort will be made to maintain patient confidentiality in accordance with federal regulation and institutional policy.

Chain of custody of biological samples: The chain of custody will be maintained for all samples throughout to completion and close out of the trial. A record of storage location will be documented. Records will be available for monitoring and audit as requested.

